7.2. Discussion of Design and Control

This is a superiority study, the main objective of which is to compare the effects of dulaglutide 0.75 and dulaglutide 1.5 mg/week (pooled), added to diet and exercise, with or without metformin and/or basal insulin, to those of placebo on glycemic control (defined as change in HbA1c) in pediatric patients with T2DM over a 26-week period.

The efficacy measure, HbA1c, was chosen as the primary objective because it is an accepted endpoint in glycemic trials in pediatric patients with T2DM.

The use of placebo for 26 weeks during the double-blind portion of the trial was considered appropriate, as no results of Phase 3 trials with dulaglutide (or any other GLP-1 RA) had been reported in the pediatric population at the time of protocol development. Thus, a placebo comparator is necessary to understand dulaglutide's true safety and effectiveness. In order to protect the safety of the patients enrolled in both arms of this trial, the double-blind period is relatively short, there are clear rescue criteria for patients with severe, persistent hyperglycemia (see Section 8.3.4) and patients are allowed to decrease basal insulin or metformin as needed if hypoglycemia occurs (for the definition of hypoglycemia, see Section 10.4.1.2.1).

The doses of dulaglutide for this trial were chosen by PK simulations (see Section 9.4).

The background therapies of diet and exercise, with or without metformin and/or basal insulin, are considered appropriate, as these are approved treatments for pediatric patients with T2DM in the US, EU, and many countries around the world.

In adults, dulaglutide has been shown to be effective in lowering HbA1c with consistent safety in the monotherapy setting (diet and exercise only) and when added to metformin and other oral anti-diabetes agents and/or short-acting or basal insulin. The decision not to maximize the doses of metformin and basal insulin was considered appropriate, as metformin at a dose of ≥ 1000 mg/day is considered an effective dose in pediatric patients. For patients using basal insulin, up-titration of insulin during the double-blind period would reduce the trial's ability to perceive a difference between the placebo and dulaglutide treatment arms and therefore is not allowed (see Section 9.8). Temporary increases in insulin dose are allowed during the trial and appropriate rescue methods exist in the protocol to ensure that patients do not continue in the double-blind portion of the trial with poor glycemic control. Patients may decrease doses of background diabetes medications at any time if hypoglycemia is noted.

According to the visit schedule, patients will be seen by physicians in the clinic approximately every 3 months, with monthly telephone visits in between the clinic visits. This is considered appropriate, as pediatric patients with T2DM are usually seen in the clinic every 3 months.

There is uncertainty in the correct sample size to have sufficient power for this study. This is due to a number of reasons: lack of experience with T2DM pediatric patients receiving GLP-1 RAs; a wide range of baseline HbA1c values; and the inclusion of patients potentially using both metformin and basal insulin in this trial. These factors will influence the variability of the treatment difference for the primary endpoint, which is mean change from baseline in HbA1c at 26 weeks. An underestimate of the variability could lead to an inconclusive study. An overestimate of the treatment variability could expose more patients than necessary to placebo and could lead to unnecessary enrollment challenges. As a consequence, an information-based sample size re-estimation may be implemented to mitigate against an inconclusive study.

To optimize statistical power to detect a meaningful treatment difference, there will be treatment group comparisons at the 26-week primary endpoint based on the pooled dulaglutide arms compared to placebo.

8. Study Population

Individuals who do not meet the criteria for participation in this study (screen failure) may be rescreened up to 2 times. The interval between re-screenings should be at least 8 weeks. Each time rescreening is performed, the individual must sign a new ICF, and will be assigned a new identification number.

Entered patients who meet all of the Inclusion Criteria and are not excluded by Exclusion Criteria will proceed to Visit 2 (randomization).

Prospective approval of protocol deviations to recruitment and enrollment criteria, also known as protocol waivers or exemptions, are not permitted.

8.1. Inclusion Criteria

Patients are eligible to be included in the study only if they meet all of the following criteria:

- [1] Are male or female children and adolescents aged 10 to <18 years at randomization.
- [2] Have T2DM as diagnosed by Global International Diabetes Foundation/International Society for Pediatric and Adolescent Diabetes (IDF-ISPAD; IDF 2011 [WWW]) criteria (see [Attachment 5](#)).
- [3] Have T2DM treated at the time of randomization with lifestyle measures (standardized diet and exercise program), with or without metformin (≥ 1000 mg/day, unless the patient has documented intolerance of metformin, in which case the highest tolerated dose will be used, and not more than the locally approved dose), and/or basal insulin therapy. Doses of metformin and basal insulin must have been stable ($\pm 15\%$) for at least 8 weeks prior to screening visit. Lifestyle measures must have been in place for at least 8 weeks prior to the screening visit.
- [4] Have HbA1c $>6.5\%$ to $\leq 11.0\%$ at screening visit, unless a patient is newly diagnosed and only treated with lifestyle measures, in which case the HbA1c should be $>6.5\%$ to $\leq 9.0\%$.
- [5] Have BMI $>85\%$ percentile of the general age- and gender-matched population for that country or region and body weight ≥ 50 kg.
- [6] Both the child or adolescent with T2DM and a parent or legal guardian are able to understand and fully participate in the activities of the clinical trial and sign their assent and consent, respectively.

8.1.1. Disease Diagnostic Criteria

For the purposes of this study, patients with T2DM are defined by the IDF-ISPAD (IDF 2011 [WWW]) criteria (see [Attachment 5](#)), the absence of diabetes-associated autoantibodies for T1DM (glutamic acid decarboxylase 65 [GAD65] autoantibodies and tyrosine phosphatase-like

insulinoma antigen 2 [IA2] antibodies), and BMI >85% percentile of the general age- and gender-matched population for that country or region at screening.

8.2. Exclusion Criteria

Patients will be excluded from study enrollment if they meet any of the following criteria:

- [7] Have known T1DM.
- [8] Have a history of diabetic ketoacidosis or hyperglycemic hyperosmolar syndrome.
- [9] Have diabetes-associated autoantibodies (GAD65 or IA2), historically or at screening.
- [10] Have a clinically significant gastric emptying abnormality, in the opinion of the investigator, or previous gastric bypass.
- [11] Have prior chronic, recurrent, or idiopathic pancreatitis; known gallbladder disease; or clinical hypertriglyceridemia associated with pancreatitis, i.e., >11.2 mmol/L (>1000 mg/dL), historically or at screening.
- [12] Have a known self or family history of multiple endocrine neoplasia (MEN) type 2A or type 2B, thyroid C-cell hyperplasia, or medullary thyroid carcinoma.
- [13] Have a serum calcitonin ≥ 20 pg/mL at screening, as determined by the central laboratory.
- [14] Have an estimated glomerular filtration rate (eGFR) < 60 mL/min at screening.
- [15] Have recurrent severe hypoglycemia or hypoglycemic unawareness as judged by the investigator.
- [16] Have blood pressure above the 99th percentile for age and gender in children OR systolic blood pressure ≥ 160 mm Hg or diastolic blood pressure ≥ 100 mmHg at screening.
- [17] Have an active or treated malignancy.
- [18] Have a hemoglobinopathy or other disorder that interferes with the accurate determination of the primary endpoint, including, but not limited to, patients with the following hemoglobin variants: HbS, HbC, HbE, HbSC, and elevated HbF.
- [19] For females of childbearing potential: Are sexually active and not on either 1 highly effective form of contraception or 2 effective forms of contraception (see [Attachment 4](#)).
- [20] For females of childbearing potential: Are pregnant or intending to become pregnant.
- [21] For females of childbearing potential: Are breastfeeding.
- [22] Are known to or are suspected of chronically abusing alcohol or drugs/narcotics.

- [23] Have any clinically significant disorder, other than T2DM, that, in the investigator's opinion, would preclude participation in the trial.
- [24] Are currently taking a class of antihyperglycemic medication other than biguanides (metformin) and/or basal insulin including but not limited to bolus insulin, a sulfonylurea, alpha-glucosidase inhibitor, DPP-IV inhibitor, GLP-1 RA, thiazolidinedione (TZD), glinide, and sodium-glucose co-transporter 2 (SGLT-2) inhibitor. Except for bolus insulin, these medications must have been stopped at least 3 months before the screening visit. Patients should not have received bolus insulin within 6 weeks of the screening visit, except as rescue treatment for management of acute medical conditions for a maximum of 14 days.
- [25] Are currently using inhaled steroids at a dose equal to or above 1000 mcg Flovent® (fluticasone propionate) daily.
- [26] Have used chronic (>14 consecutive days) oral steroids within the last 60 days or more than 20 days use within the past year.
- [27] If currently taking medications indicated to treat a psychiatric condition (including, but not limited to depression, anxiety, bipolar disease, attention deficit hyperactivity disorder [ADHD], and schizophrenia); and if doses have not been stable ($\pm 10\%$) for at least 3 months prior to screening, and/or if there is an intention to change or add new medications during the trial.
- [28] Have used any prescription weight loss medication(s) within 30 days of screening or intend to use chronically during the clinical trial. These include, but are not limited to, the following: Contrave® (naltrexone/bupropion), Saxenda® (liraglutide), Xenical® (orlistat), Meridia® (sibutramine), Acutrim® (phenylpropanolamine), Sanorex® (mazindol), Adipex® (phentermine), BELVIQ® (lorcaserin), Qsymia™ (phentermine/topiramate combination), or similar over-the-counter medications (e.g., alli®).
- [29] Are investigator site personnel directly affiliated with this study and/or their immediate families. Immediate family is defined as a spouse, parent, child, or sibling, whether biological or legally adopted.
- [30] Are Lilly employees or are employees of third-party organizations (TPOs) involved in the study who require exclusion of their employees.
- [31] Are currently enrolled in any other clinical trial involving an investigational product (IP) or any other type of medical research judged not to be scientifically or medically compatible with this study.
- [32] Have participated within the last 30 days in a clinical trial involving an IP other than the IP used in this study. If the previous IP has a long half-life, 3 months or 5 half-lives (whichever is longer) should have passed.
- [33] Have previously completed or withdrawn from this study or any other study investigating dulaglutide. This exclusion criterion does not apply to patients who are rescreened prior to randomization.

8.2.1. Rationale for Exclusion of Certain Study Candidates

Exclusion Criteria [7] to [9] eliminate patients with T1DM or those in whom HbA1c cannot be accurately assessed.

Exclusion Criteria [10] to [17] eliminate patients with conditions that may pose a risk for morbidity or mortality.

Exclusion Criterion [18] eliminates patients with conditions that interfere with the assessment of the primary endpoint.

Exclusion Criteria [19] to [21] eliminate female patients at risk for becoming pregnant or who are nursing.

Exclusion Criteria [22] to [23] eliminate patients with conditions making them more likely to not complete the clinical trial.

Exclusion Criteria [24] to [28] eliminate patients taking drugs that may interfere with assessment of the primary endpoint.

Exclusion Criteria [29] to [33] reduce the potential bias that may be introduced at the study site.

8.3. Discontinuations

8.3.1. Discontinuation of Inadvertently Enrolled Patients

The criteria for enrollment must be followed explicitly. If Lilly or the investigator identifies a patient who did not meet enrollment criteria and was inadvertently enrolled, a discussion must occur between the Lilly clinical research physician (CRP) or designee and the investigator to determine if the patient may continue in the study, with or without study drug. The investigator must obtain documented approval from the Lilly CRP (or designee) to allow the inadvertently enrolled patient to continue in the study with or without treatment with study drug.

In general, inadvertently enrolled patients must continue in the study, with or without study drug, unless they withdraw their informed consent, are lost to follow-up, have T1DM, have a hemoglobinopathy or other disorder that interferes with the accurate determination of the primary endpoint, or are pregnant or breastfeeding.

Study drug will be continued if the Lilly CRP (or designee) and the investigator agree that it is acceptable for a patient to continue to receive study drug. Patients with significant safety concerns will not be continued on study drug. For patients continuing on study drug, a clinical justification will be provided. If the Lilly CRP (or designee) believes that it is inappropriate for the patient to continue to receive study drug, it will be discontinued, but the patient will remain in the study, and attend all scheduled visits, and be evaluated for all efficacy and safety endpoints for the duration of the study.

8.3.2. Discontinuation of Investigational Product

Patients will be discontinued from study drug if they are confirmed to have the following Exclusion Criteria:

- [7] to [9]—T1DM (the patient will also be discontinued from the trial)
- [11] to [12]—safety concerns, for example, patients will be discontinued from study drug if they develop confirmed pancreatitis (if not confirmed, study drug may be restarted) (see Section 10.4.1.2.2).
- [18]—unable to assess primary endpoint (the patient will also be discontinued from the trial)
- [19] to [21]—pregnancy or breastfeeding (the patient will also be discontinued from the trial)
- [29] to [33]—potential bias.

The patient should be discontinued from study drug for abnormal liver tests when the patient meets 1 of the following conditions (and after consultation with the Lilly CRP or designee):

- Alanine aminotransferase (ALT) or aspartate aminotransferase (AST) $>6 \times$ upper limit of normal (ULN)
- ALT or AST $>5 \times$ ULN for more than 2 weeks
- ALT or AST $>3 \times$ ULN and total bilirubin level $>2 \times$ ULN or prothrombin time $>1.5 \times$ ULN
- ALT or AST $>3 \times$ ULN with the appearance of fatigue, nausea, vomiting, right upper-quadrant pain or tenderness, fever, rash, and/or eosinophilia ($>5\%$).
- Alkaline phosphatase (ALP) $>3 \times$ ULN
- ALP $>2.5 \times$ ULN and total bilirubin $>2 \times$ ULN
- ALP $>2.5 \times$ ULN with the appearance of fatigue, nausea, vomiting, right upper-quadrant pain or tenderness, fever, rash, and/or eosinophilia ($>5\%$)

The most common AEs experienced by patients receiving dulaglutide are gastrointestinal symptoms known to be associated with GLP-1 RA therapy. These symptoms may be self-limited. Patients judged by the investigator unable to tolerate study drug (e.g., intractable nausea, vomiting and diarrhea) should temporarily (or permanently) discontinue study drug, but remain in the study.

Patients unable to tolerate the study drug after a potential dosage change at Week 4 may temporarily go back to the previously assigned study drug. However, they should be encouraged to take their assigned study drug, if possible.

Study drug should be temporarily discontinued in any individual suspected of having a severe or serious allergic reaction to study drug or other serious safety concerns. Study drug may be restarted when/if it is safe to do so, in the opinion of the investigator.

Patients who permanently discontinue the study drug early will receive another glucose-lowering intervention and continue to attend all scheduled visits and undergo all scheduled procedures as shown in the Study Schedule ([Attachment 1](#)). The new glucose-lowering intervention must not be another GLP-1 receptor antagonist or DPP-IV inhibitor.

8.3.3. Patient Discontinuation from the Study

Patients will be discontinued from the study under the following circumstances:

- Patient Decision
 - The patient (and/or parent or legal guardian) withdraws his/her/their consent
- Lost to Follow-Up
 - A patient will be considered lost to follow-up if he/she repeatedly fails to return for scheduled visits and is unable to be contacted by the study site.
 - Site personnel are expected to make diligent, repeated attempts to contact patients who fail to return for a scheduled visit or who were, otherwise, unable to be followed up by the site. Site personnel, or an independent third party, may attempt to collect the vital status of the patient within legal and ethical boundaries for all patients randomized, including those who did not get study drug.
- Inadvertent Enrollment
 - Patients found to have T1DM, a hemoglobinopathy or other disorder that interferes with the accurate determination of the primary endpoint, or are pregnant or breastfeeding at the time of enrollment, will be discontinued.
- Pregnancy and Breastfeeding
 - Patients found to be pregnant or breastfeeding during the trial will be discontinued.

Patients who discontinue the study early will have end-of-study procedures performed as shown in the Study Schedule ([Attachment 1](#)) and will also have a follow-up safety visit 30 days after study discontinuation (Visit 801).

8.3.4. Rescue for Hyperglycemia

Patients will be considered for rescue treatment in the following circumstances:

- Weeks 0-6: average FBG >15 mmol/L (270 mg/dL) over at least a 2-week period (at least 4 values/week must be available)
- Weeks 7-12: average FBG >13.3 mmol/L (240 mg/dL) over at least a 2-week period (at least 4 values/week must be available)
- Weeks 13-26: average FBG >11.1 mmol/L (200 mg/dL) over at least a 2-week period (at least 4 values/week must be available)
- Weeks 26-52: average FBG >11.1 mmol/L (200 mg/dL) over at least a 2-week period (at least 4 values/week must be available)

If the patient does not meet the above criteria, an investigator may rescue a patient if there is other documented evidence that the patient is experiencing severe, persistent hyperglycemia over at least 2 weeks.

Rescue therapy will consist of approved therapy for T2DM pediatric patients (i.e., metformin and/or insulins). The use of GLP-1 RAs and DPP-IV inhibitors for rescue therapy is not allowed.

Patients may be treated with short-term (up to 2 weeks) of unlimited metformin or insulin therapy with continuation of study drug (see Section 9.8). This will not constitute rescue.

During the double-blind period (Weeks 0-26), in patients not previously rescued, rescue will have occurred if:

- A patient treated with lifestyle + study drug at baseline receives metformin and/or insulin for more than 2 weeks
- A patient treated with metformin + study drug at baseline receives treatment with >15% more metformin and/or insulin at any dose for more than 2 weeks
- A patient treated with basal insulin + study drug at baseline receives treatment with >15% more basal insulin and/or another type of insulin at any dose for more than 2 weeks

During the open label period, (Weeks 27-52), in patients not previously rescued, rescue will have occurred if there is addition of a new medication as described below and not with changes in dosing of already administered medication(s):

- A patient treated with lifestyle + dulaglutide at Week 26 receives metformin and/or insulin at any dose for more than 2 weeks
- A patient treated with metformin + dulaglutide at Week 26 receives treatment with insulin at any dose for more than 2 weeks
- A patient treated with basal insulin + dulaglutide at Week 26 receives treatment with another type of insulin at any dose for more than 2 weeks

If patients undergo rescue for hyperglycemia, they will remain on study drug, and will continue in the trial, unless the investigator believes they should be discontinued from study drug.

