9.8. Concomitant Therapy

The only allowed concomitant chronic diabetes therapies are metformin and basal insulin.

Use of metformin:

- Either metformin immediate release or metformin extended release may be used during the study if indicated for the treatment of children in the local geography; however, the type of metformin should remain the same throughout the study, if possible. If a change in type of metformin (i.e., conversion of extended release to immediate release or vice versa) is required, the investigator should determine the most appropriate clinically equivalent metformin dose.
- The dose of metformin must remain stable during the double-blind period of the trial unless:
 - The patient stops tolerating metformin.
 - The patient develops an absolute or relative contraindication to metformin use (according to the local metformin label).
 - The patient experiences hypoglycemia (for the protocol definition of hypoglycemia, see Section 10.4.1.2.1).
- During the double-blind period, in the event of acute illness with hyperglycemia, the dose of metformin may be increased >15% of the baseline dose for 2 weeks and/or unlimited insulin therapy may be used with metformin for up to 2 weeks. After that period, the metformin dose should be back to the baseline dose and insulin therapy should be stopped. This does not constitute rescue.

Use of basal insulin:

- Basal insulin may include: Neutral Protamine Hagedorn (NPH) insulin, insulin detemir, insulin glargine, or any insulin whose labeling states that it is long-acting and used once or twice a day as basal insulin.
- The type of basal insulin should remain the same throughout the study, if possible.
- During the double-blind phase (Weeks 0-26), the dose of basal insulin should remain no higher than the dose at randomization (Visit 2) +15%.
 - The dose may be decreased if the patient has experienced hypoglycemia. In that case, the patient's basal insulin dose will be decreased until hypoglycemia is absent.

- If the patient experiences acute illness with hyperglycemia, unlimited insulin therapy may be used for up to 2 weeks. After that time, the patient's basal insulin dose should be at the baseline dose (+15%) and other insulins (if used) should be stopped. This does not constitute rescue.

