- In patients on basal insulin, especially those who are in good glycemic control (HbA1c <7.0%), investigators should pay close attention as to whether hypoglycemia is occurring and whether the basal insulin dose needs to be reduced.
- A suggested scheme for adjusting basal insulin in response to hypoglycemia is given below.

If patient has 2 FBGs in a week of:	Adjust basal insulin dose:
≤50 mg/dL (<2.8 mmol/L)	Decrease by at least 8 units or 10%, whichever is greater
>51-70 mg/dL (>2.8-3.9 mmol/L)	Decrease by 5 units or 5%, whichever is greater
>71-80 mg/dL (>3.9-4.4 mmol/L)	Decrease by 5 units
>80 mg/dL (>4.4 mmol/L)	No adjustment

As a reminder, during the double-blind period, if a patient is experiencing severe, persistent hyperglycemia, the patient should be considered for rescue (Section 8.3.4). Patients who are rescued will continue in the study and will continue to take study drug (unless the investigator determines that they should not).

With the exception of prescription weight loss medications, all non-diabetes concomitant therapies that are part of routine medical care that the patient requires are allowed and can be used during the study. High-dose inhaled or oral steroids should be used only as long as medically necessary. Doses of psychiatric medication should remain stable.

Although efforts should be made not to change the basal insulin dose more than 15% during the double-blind period, during the open-label period (as this period is primarily assessing safety) if basal insulin must be increased, it may be, without calling it "rescue." For patients taking basal insulin, rescue will be defined as adding another type of insulin. During the open-label period, patients who are rescued will continue in the study and will continue to take study drug (unless the investigator determines that they should not).

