- c The metformin and basal insulin doses established at Visit 2 should not vary more than 15% during the double-blind period (until Visit 9). Patients may receive unlimited insulin for hyperglycemia for up to 2 weeks and it will not be deemed “rescue.” The basal insulin dose may be recalculated at Visit 9 and may be increased as needed during the open-label period. Metformin and basal insulin may be decreased at any time if the patient has hypoglycemia.
- d In females of childbearing potential. If pregnancy is suspected, a local urine pregnancy test should be performed and a serum pregnancy test sent to the central laboratory.
- e Includes SMBG results, hypoglycemic events, AE information, date, and exact time of every study drug injection and date of last menstrual period (for females).
- f At Visits 1 and 2, collect last menstrual period only. At Visit 801, collect AEs and last menstrual period only.
- g Glucometer, blood glucose test strips, lancets, alcohol swabs, and lancing device as needed. Patients may be trained at screening and will be trained at randomization. Additional training may occur as needed.
- h Using the demonstration pen, which does not have a needle and is filled with air. Training at Visit 1 is recommended but not required. Training at Visit 2 is required.
- i Complete baseline assessments before using IWRS.
- j Optional dispensing visit for investigational product.
- k If it is the patient’s dosing day, study drug will be administered prior to performing other visit procedures.
- l Standard blood chemistries and hematology are shown in [Attachment 2](#). They include eGFR, which will be calculated by the central laboratory.
- m Serum hormones should be drawn in the morning (fasting) and include: cortisol, IGF-1, prolactin, LH, estradiol (females and males) and testosterone (males only).
- n The patient should come to the clinic to have this performed if pregnancy is suspected. If a local urine pregnancy test is performed, draw blood for serum pregnancy test at the same time and send to central laboratory.

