5.11.1. Primary Analysis

Two primary estimands will be formed to compare the effect between All Dula and Placebo at Week 26. Each estimand will be tested with 2-sided alpha=0.05. The 2 estimands are derived from the ITT population for the primary efficacy endpoint:

1. Efficacy estimand from ITT population by censoring the post-rescue data
2. Treatment regimen estimand from ITT population regardless of rescue status or treatment adherence

The efficacy estimand measures the benefit of the assigned study treatment in the absence of the confounding effects of additional or alternative antihyperglycemic agents and regardless of compliance with study treatment. All scheduled post-first-dose-visit measurements up to Week 26 (Visit 9) inclusive will be used. The MMRM model mentioned in Section 5.2 will be fitted by replacing the baseline HbA1c strata with the baseline HbA1c as a covariate.

This method is chosen as the primary analysis as it is recommended by the National Research Council report (NRC 2010). This primary analysis is under missing at random (MAR) assumption and such an assumption often makes sense for the primary analysis (Little et al. 2012). Censoring the postrescue data minimizes the confounding rescue therapy's effect on the studied drug (O'Neill and Temple 2012).

The treatment regimen estimand measures the benefit of the assigned study treatment regardless of the use of any additional or alternative antihyperglycemic agents or compliance with study treatment. An ANCOVA model will be applied as the primary analysis to the complete data using multiple imputation (Section 5.11.3).

- Primary estimand for the FDA: treatment regimen estimand that will include post-rescue data
- Primary estimand for EMA: efficacy estimand excluding post-rescue data, and those patients treated with diet and exercise only who are metformin naïve from ITT population
- In general, for all other audiences: efficacy estimand that will not include post-rescue data (i.e., will censor the nonmissing, post-rescue data).

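### The double-blind rescue list in Protocol 8.3.4 omits metformin for patients on basal insulin and assigns no clear row to metformin plus basal insulin

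*Protocol*

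**What the plan says.** Protocol 8.3.4 first says what rescue is: "Rescue therapy will consist of approved therapy for T2DM pediatric patients (i.e., metformin and/or insulins"). It then lists when rescue has occurred in Weeks 0 to 26, in three rows by baseline background.

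- Row 1, lifestyle: metformin and/or insulin for more than 2 weeks.
- Row 2, metformin: a patient "treated with metformin + study drug at baseline receives treatment with >15% more metformin and/or insulin at any dose for more than 2 weeks".
- Row 3, basal insulin: a patient "treated with basal insulin + study drug at baseline receives treatment with >15% more basal insulin and/or another type of insulin at any dose", again for more than 2 weeks.

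Eligible patients may be on metformin, basal insulin, both or neither (Protocol 8.1, criterion 3). Metformin use and insulin use are separate yes/no stratification factors (Protocol 9.3, SAP 5.2).

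Protocol 9.8 lets metformin and insulin rise for up to 2 weeks in acute illness, and then: "After that period, the metformin dose should be back to the baseline dose and insulin therapy should be stopped". For basal insulin, "the dose of basal insulin should remain no higher than the dose at randomization (Visit 2) +15"%. Footnote c of the study schedule adds: "The metformin and basal insulin doses established at Visit 2 should not vary more than 15% during the double-blind period".

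SAP 5.11.1 describes the efficacy estimand as the benefit of assigned treatment "in the absence of the confounding effects of additional or alternative antihyperglycemic agents". Its only stated censoring trigger is rescue. The SAP gives no rescue definition by regimen.

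**The concern.** Rows 1 and 2 both count metformin; row 3 does not. An investigator can thus give a basal insulin patient a drug that 8.3.4 itself calls rescue therapy, and by the list rescue will not have occurred. There is a second permitted route: a patient who permanently stops study drug is to receive another glucose-lowering intervention (Protocol 8.3.2), and metformin is not excluded. So this is not only a matter of protocol deviations.

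The combination regimen is eligible, yet no row names it.

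Rescue status feeds several analyses: censoring in the efficacy estimand, which is primary for EMA and for all audiences other than FDA (SAP 5.11.1); censoring in the primary hypoglycemia analyses (SAP 5.2 and 5.15.2.1); the responder sensitivity analysis, where rescued patients count as failures (SAP 5.12.2); and rescue incidence and time to rescue (SAP 5.15.5). If the list is applied as it stands, some HbA1c data affected by added metformin stay in the efficacy estimand, and rescue is undercounted in basal insulin patients. The important-deviation list (SAP 5.7) exempts metformin, and the per-protocol analyses have been dropped (SAP 3, Version 7), so neither catches the case.

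**Working it through.** The plan gives no figure on this point to reproduce. The check is an enumeration of the list, followed by a scale for its effect.

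**Step 1. Apply the three rows to each background and each change lasting more than 2 weeks.** Row 2 can be read in two ways: as covering metformin without insulin (rows as steps of background therapy), or as covering any patient on metformin (literal).

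| Baseline background | Sustained change | Row met, step reading | Row met, literal reading |
|---|---|---|---|
| Lifestyle only | new metformin or new insulin | 1 | 1 |
| Metformin | metformin up >15%, or new insulin | 2 | 2 |
| Basal insulin only | basal up >15%, or other insulin | 3 | 3 |
| Basal insulin only | new metformin | none | none |
| Metformin + basal insulin | basal up >15%, or other insulin | 3 | 2 and 3 |
| Metformin + basal insulin | metformin up >15% | none | 2 |
| Metformin + basal insulin | no change | none | 2 |

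New metformin on basal insulin alone meets no row under either reading. For the combination, the step reading misses the metformin increase. The literal reading catches it, but row 2 also counts insulin at any dose, so every combination patient is rescued from the start without any change. That cannot be intended.

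**Step 2. Scale.** Inputs from the documents:

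- Original plan (Protocol 12.1): 120 completers in three equal arms, so 80 pooled dulaglutide and 40 placebo; SD 1.0; difference 0.65.
- 2019 re-estimation (SAP 5.1): SD 1.4, difference 0.8, 10% missing. 150 × 0.9 = 135, so 90 and 45.

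Assumption, not in the documents: added metformin lowers one patient's Week 26 HbA1c by d = 0.2 to 1.0 points.

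Standard error of a simple difference in means:

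- Original: 1.0 × √(1/80 + 1/40) = 0.194.
- Re-estimation: 1.4 × √(1/90 + 1/45) = 0.256.

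Shift in the treatment difference from one uncensored placebo patient:

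- Original: d/40 = 0.005 to 0.025 points, which is 0.8% to 3.8% of 0.65, or 0.03 to 0.13 SE.
- Re-estimation: d/45 = 0.004 to 0.022 points, which is 0.6% to 2.8% of 0.8, or 0.02 to 0.09 SE.

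One dulaglutide patient moves the estimate the other way by half as much: d/80 = 0.0025 to 0.0125, or d/90 = 0.0022 to 0.0111. If a proportion p is affected in every arm, the shift is p × d − p × d = 0.

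Placebo patients needed for a shift of one SE, with none on dulaglutide:

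- At d = 1.0: 0.194 × 40 = 7.7, about 8 of 40; 0.256 × 45 = 11.5, about 12 of 45.
- At d = 0.5: twice as many, 15.5 and 23.0.

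**Step 3. Power, as an illustration.** With 40 and 80 completers, SD 1.0 and difference 0.65, power is 91.9%, in line with the stated figure of at least 90%. Suppose the affected share is 2% to 10% higher on placebo and d is 0.5 to 1.0. The difference becomes 0.65 − 0.02 × 0.5 = 0.64 at best and 0.65 − 0.10 × 1.0 = 0.55 at worst, with power of 91.1% and 81.1%. The worst case needs 4 of 40 placebo patients and none on dulaglutide, each with a full 1.0-point effect.

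**The case against.** Four points weigh against the concern.

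- **Row 2 can reach the combination patient.** A patient whose metformin rises was on metformin at baseline. Row 2 does not say without insulin, and the rows are not declared exclusive. This stands: a reader might infer that any metformin increase in a basal insulin patient is outside rescue as written, and the text does not support that. But the same literal reading flags every combination patient through the any-dose insulin clause, so the case is undetermined rather than covered.
- **Censoring might happen anyway.** A reader might infer that the affected data are certainly left uncensored. The documents do not establish this. Protocol 12.2.1 (for other efficacy measures and hypoglycemia) and SAP 5.2 (for hypoglycemia) censor after any rescue medication, and 8.3.4 calls metformin rescue therapy. The Version 7 changes in SAP 3, speaking of a listing, indicate that rescue therapy is recorded on the case report form. The list is introduced with an if, not an only if. This stands as to outcome. It does not repair the list, and two programmers could derive different flags.
- **Conduct rules limit the case.** Section 9.8 and footnote c require a stable dose, so a sustained metformin rise not given as rescue would be a deviation. SAP 5.8 also tabulates antihyperglycemic use as rescued and nonrescued, so added metformin is visible. Both stand, but neither sets the censoring date.
- **Basal insulin changes and the open-label list are not in dispute.** Changes of 15% or less are permitted background adjustment. For the open-label period 9.8 makes a deliberate choice: "For patients taking basal insulin, rescue will be defined as adding another type of insulin".

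**Conclusion.** The point holds, as a minor one. For metformin newly started on basal insulin alone, the double-blind list gives the wrong rescue status: it contradicts the section's own statement of what rescue therapy is and the estimand described in SAP 5.11.1. For a sustained metformin increase on metformin plus basal insulin, the list does not determine the status.

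The expected effect is very small. The documents give no count of affected patients. The rationale for the Section 12.2.6 changes in Protocol Attachment 7 says that, on blinded review, too few patients were rescued or off study drug with an endpoint measurement for a meaningful analysis; the cases here could only be a fraction of such a group. An excess on placebo shrinks the difference, which is conservative for superiority. The sizes rest on the assumed 0.2 to 1.0 point metformin effect and on a simple difference of means instead of the MMRM.

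A reader might infer that the primary conclusion is at risk. The documents do not support that: even at 1.0 point per patient, about 8 of 40 (or 12 of 45) placebo patients and none on dulaglutide would be needed to move the estimate by one SE. The FDA treatment regimen estimand keeps post-rescue data and is unaffected.

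**What to change.** In the double-blind list of Protocol 8.3.4, limit row 2 to patients on metformin without basal insulin. Let row 3 cover basal insulin with or without metformin, and count any of these as rescue when it lasts more than 2 weeks:

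- basal insulin more than 15% above the baseline dose;
- any other type of insulin;
- metformin more than 15% above the baseline dose;
- any metformin, if the patient took none at baseline.

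Without a protocol amendment, state this derivation of the rescue flag and censoring date in SAP 5.11.1 and 5.15.5. Then check it, blinded, against the recorded metformin and insulin doses of basal insulin patients before the primary database lock.

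The cost is one derivation sentence and a small blinded check, with no new data collection. The row wording can go into the next amendment.
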